### 9.7.4 Data Analysis

All pre-specified analyses will be described in a Statistical Analysis Plan.

Demographics, subject disposition, and screening and baseline characteristics will be summarized in each population.

### 9.7.5 Interim Analysis

No interim analysis is planned. However, an interim analysis may be performed to examine early data, if appropriate.

## 9.8 EFFICACY ANALYSIS

### 9.8.1 Primary Efficacy Endpoint

The primary efficacy analysis is of the CRISS at Week 24 for subjects administered belumosudil 200 mg BID in the mITT Population.

### 9.8.2 Secondary Efficacy Endpoints

Secondary efficacy analyses of belumosudil 200 mg BID performed on the mITT Population are:

- CRISS at Weeks 8, 16, 36, and 52
- The following analyses for Week 24:
  - mRSS
  - FVC
  - Physician Global Assessment
  - Patient Global Assessment
  - SHAQ-DI
- The following analyses at Weeks 8, 16, 36, and 52 compared to baseline:
  - mRSS
  - FVC
  - Physician Global Assessment
  - Patient Global Assessment
  - SHAQ-DI

### 9.8.3 Exploratory Analyses

- [REDACTED]
- [REDACTED]
- [REDACTED]
- [REDACTED]
- [REDACTED]

### 9.8.4 Analysis Method

Descriptive statistics will be provided for all endpoints by visit as described above.

## 9.9 SAFETY ANALYSES

Treatment exposure will be summarized.

The TEAEs will be evaluated using CTCAE v5.0. A single cohort of 12 to 20 subjects will receive belumosudil 200 mg PO BID.

The TEAEs will be summarized using Medical Dictionary of Regulatory Activities (MedDRA; Version 21.0 or higher), System Organ Class (SOC) and Preferred Term (PT), classified from verbatim terms. The incidence and percentage of subjects with at least 1 occurrence of a PT will be included, according to the most severe grade using a 5-point scale (mild, moderate, severe, life-threatening, or death). The number of events per PT will also be summarized. Causality (relationship to study treatment) will be summarized separately.

Adverse events, SAEs, related AEs, related SAEs, Grade  $\geq 3$  AEs, related Grade  $\geq 3$  AEs, and AEs leading to withdrawal, or treatment discontinuation will be summarized according to SOC and PT. Adverse events will also be presented in listings. Duration of AEs will be determined and included in listings, along with action taken and outcome.

Laboratory results will be graded. Incidence of laboratory abnormalities will be summarized. The worst on-study grade after the first dose of study drug will be summarized. The incidence of Grade  $\geq 3$  laboratory abnormalities under treatment and shifts in toxicity grading from baseline to highest-grade post-baseline will be displayed.

Vital sign measurements and ECGs will be summarized at each scheduled time point using descriptive statistics and included in data listings.

## 9.10 PHARMACOKINETIC ANALYSES

No PK analysis will be performed in this study.

## 9.11 PHARMACODYNAMIC ANALYSES

Changes in biomarkers of endothelial cell dysfunction, fibrosis, immune system function, and cytokine alterations from subjects receiving belumosudil will be analyzed as will histology and gene expression from skin biopsies taken from subjects at baseline, Week 24, and Week 52.

## **9.12 DATA QUALITY ASSURANCE**

Accurate and reliable data collection will be ensured by verification and cross check of the eCRFs against the Investigator's records by the study monitor (source document verification) and by the maintenance of a drug-dispensing log by the Investigator. Collected data will be entered into a computer database and subject to electronic and manual quality assurance procedures.

## 10. REGULATORY OBLIGATIONS

This study will be conducted in compliance with Good Clinical Practice (GCP), including International Conference on Harmonisation of Technical Requirements for Registration of Pharmaceuticals for Human Use, and in general, consistent with the most recent version of the Declaration of Helsinki. In addition, the Investigator agrees to adhere to all applicable local laws and regulatory requirements relevant to the use of new therapeutic agents in the countries involved.

The study is to be conducted in compliance with the protocol. The appropriate IRBs/IECs must approve the protocol and any amendments, and the subject ICF form before implementation.

Freely given written informed consent must be obtained from every subject before participation in this clinical trial. The rights, safety, and well-being of participating subjects are the most important considerations and should prevail over interests of science and society.

Study personnel involved in conducting this trial will be qualified by education, training, and experience to perform their respective task(s). This trial will not use the services of study personnel where sanctions have been invoked or where there has been scientific misconduct or fraud (e.g., loss of medical licensure, debarment).

## 11. ETHICAL ASPECTS

### 11.1 LOCAL REGULATIONS

The study must fully adhere to the principles outlined in Guideline for Good Clinical Practice ICH E6(R2) Integrated Addendum to ICH E6(R1) (March 2018), and in general, be conducted in a manner consistent with the most recent version of the Declaration of Helsinki. The Investigator will ensure that the conduct of the study complies with the basic principles of GCP as outlined in the current version of 21 CFR, subpart D, Part 312, “Responsibilities of Sponsors and Investigators”, Part 50, “Protection of Human Subjects”, and Part 56, “Institutional Review Boards”.

### 11.2 INFORMED CONSENT

Sample ICFs will be supplied to each site. Kadmon Corporation or its designee must review any ICF prior to submission for review by the IRB/IEC. The final IRB/IEC-approved document must be provided to Kadmon Corporation for regulatory purposes.

It is the responsibility of the Investigator, or a person designated by the Investigator, to obtain written informed consent from each subject (or the subject's legally authorized representative) participating in this study after adequate explanation of the aims, methods, anticipated benefits, and potential hazards of the study in accordance with federal and state regulations. In the case where the subject is unable to read, an impartial witness should be present during the entire informed consent discussion. After the subject has orally consented to participation in the trial, the witness' signature on the form will attest that the information in the ICF was accurately explained and understood. A copy of the ICF must be provided to the subject. If applicable, it will be provided in a certified translation of the local language.

The eCRF for this study contains a section for documenting informed subject consent, and this must be completed appropriately. Signed ICFs must remain in each subject's study file and must be available for verification by study monitors at any time. If new safety information results in changes in the risk/benefit assessment, the consent form should be reviewed and updated as necessary. All subjects (including those already being treated) should be informed of the new information, should be given a copy of the revised form, and should give their consent to continue in the study.

### **11.3 INSTITUTIONAL REVIEW BOARD**

This study is being conducted under a United States IND application. This protocol (and any modifications) and appropriate consent procedures must be reviewed and approved by an IRB/IEC. This board must operate in accordance with the current federal or local regulations. The Investigator will send a letter or certificate of IRB/IEC approval to Kadmon Corporation (or designee) before subject enrollment and whenever subsequent modifications to the protocol are made.

### **11.4 FUTURE USE OF SUBJECT SAMPLES**

Not all of the tissue and blood components obtained during this study may be required for the tests that are part of the clinical trial. Following the conclusion of the study, the samples may be used for additional research. This research will help to understand disease subtypes, drug response and toxicity, and possibly identify new drug targets or biomarkers that predict subject response to treatment. The use of the samples for internal research will be done according to the guidelines defined by the FDA guidance for *In Vitro Diagnostic Device Studies Using Leftover Human Specimens that are Not Individual Identifiable* (issued April 25, 2006) and/or the European Medicines Agency Reflection Paper on Pharmacogenetic Samples, Testing and Data Handling (EMEA/CHMP/PGxWP/201914/2006).

If a subject requests destruction of their tissue and blood samples and the samples have not yet been de-identified, Kadmon Corporation will destroy the samples as described in this FDA guidance. Kadmon Corporation will notify the Investigator in writing that the samples have been destroyed.

Once all samples have been analyzed for additional research, the samples will be discarded and will not be stored for future research.

## 12. CONDITIONS FOR MODIFYING THE PROTOCOL

Protocol modifications will be reviewed and approved by Kadmon Corporation representatives.

All protocol modifications must be submitted to the IRB/IEC for information and approval in accordance with local requirements, and to regulatory agencies if required. Approval must be obtained before any changes can be implemented, except for changes necessary to eliminate an immediate hazard to study subjects, or when the change involves only logistical or administrative aspects of the trial (e.g., change in monitor, change of telephone number).

### **13. CONDITIONS FOR TERMINATING THE STUDY**

Kadmon Corporation has the right to terminate the study at any time. In terminating the study, Kadmon Corporation and the Investigator will ensure that adequate consideration is given to the protection of the subjects' interests.

## 14. STUDY DOCUMENTATION, CRFS AND RECORD KEEPING

### 14.1 INVESTIGATOR'S FILES AND RETENTION OF DOCUMENTS

The Investigator must maintain adequate and accurate records to enable the conduct of the study to be fully documented and the study data to be subsequently verified. These documents should be classified into 2 separate categories as follows: (1) Investigator's study files and (2) subject clinical source documents.

The Investigator's study file will contain the protocol and protocol amendments, eCRFs, query forms, IRB/IEC, and governmental approval with correspondence, sample ICF, drug records, staff curriculum vitae and authorization forms, and other appropriate documents and correspondence.

Subject clinical source documents (usually predefined by the project to record key efficacy and safety parameters independent of the eCRFs) may include subject hospital/clinic records, physician and nurse's notes, appointment book, original laboratory reports, ECG, electroencephalogram, X-ray, pathology and special assessment reports, signed ICFs, consultant letters, and subject screening and enrollment logs. The Investigator must keep these 2 categories of documents on file for at least 2 years following the marketing application approval date for the study drug and for the indication being investigated or for 2 years after the investigation is discontinued and the FDA notified. After that period of time, the documents may be destroyed subject to local regulations with prior written permission from Kadmon Corporation. If the Investigator wants to assign the study records to another party or move them to another location, Kadmon Corporation must be notified in advance.

If the Investigator cannot guarantee the archiving requirement at the study site for any or all of the documents, special arrangements must be made between the Investigator and Kadmon Corporation to store these in a sealed container outside of the study site so that they can be returned sealed to the Investigator in case of a regulatory audit. When source documents are required for the continued care of the subject, appropriate copies should be made for storing outside of the study site.

### 14.2 SOURCE DOCUMENTS AND BACKGROUND DATA

Upon request, the Investigator will supply Kadmon Corporation with any required background data from the study documentation or clinic records. In case of special

problems or governmental queries or requests for audit inspections, it is also necessary to have access to the complete study records, provided if subject confidentiality is protected.

#### **14.3 AUDITS AND INSPECTIONS**

The Investigator should understand that source documents for this study should be made available to appropriately qualified personnel from the Kadmon Corporation Quality Assurance Unit (or designee), or to health authority inspectors after appropriate notification. The verification of the eCRF data must be by direct inspection of source documents.

#### **14.4 ELECTRONIC CASE REPORT FORMS**

Clinical trial data for this study will be captured on electronic eCRF. The Investigator agrees to provide all information requested on the eCRF in an accurate manner according to instructions provided. Electronic CRFs are designed for computer processing and analysis. The Investigator should ensure the accuracy, completeness, and timeliness of the data reported to Kadmon Corporation (or designee) in the eCRF and in all required reports.

An eCRF is required to be submitted for every subject who receives any amount of study drug. This includes submission of retrievable data on subjects who withdraw before completion of the study. The eCRFs must be reviewed for completeness and accuracy, and electronically signed where indicated, by the principal Investigator or authorized delegate from the study staff. If a subject stops treatment or terminates from the study, the dates and reasons must be noted on the eCRF.

## **15. MONITORING OF THE STUDY**

It is understood that the responsible monitor (or designee) will contact and visit the Investigator regularly and will be allowed on request to inspect the various records of the trial (eCRFs and other pertinent data) provided subject confidentiality is maintained in accordance with local requirements.

It will be the monitor's responsibility to inspect the eCRFs at regular intervals throughout the study, to verify the adherence to the protocol and the completeness, consistency, and accuracy of the data being entered on them. The monitor should have access to laboratory test reports and other subject records needed to verify the entries on the eCRF. The Investigator (or designee) must agree to cooperate with the monitor to ensure that any problems detected in the course of these monitoring visits are resolved.

## **16. CONFIDENTIALITY OF TRIAL DOCUMENTS AND SUBJECT RECORDS**

The Investigator must ensure that subjects' anonymity will be maintained and that their identities are protected from unauthorized parties. On eCRFs or other documents submitted to Kadmon Corporation, subjects should be identified by an identification code and not by their names. The subjects' personal information should be redacted on all source documents prior to submission to Kadmon Corporation (or designee). The Investigator should keep a subject enrollment log showing codes, names, and addresses. The Investigator should maintain documents not for submission to Kadmon Corporation (e.g., subjects' written consent forms) in strict confidence.

## **17. PUBLICATION OF DATA AND PROTECTION OF TRADE SECRETS**

The results of this study may be published or presented at scientific meetings. The Investigator agrees to submit all manuscripts or abstracts to Kadmon Corporation for review at least 30 days before submission. This allows Kadmon Corporation to protect proprietary information and to provide comments based on information from other studies that may not yet be available to the Investigator.

In the event that Kadmon Corporation coordinates a publication or presentation of study results from all study sites, the participation of Investigator or other representatives of study site as a named author shall be determined in accordance with Kadmon Corporation policy and generally accepted standards for authorship.

## 19. APPENDIX A: SCHEDULE OF ASSESSMENTS

Assessment	Screening Visit	Week 1 (Baseline)	End of Week 2	End of Week 4	End of Week 8	End of Week 12	End of Week 16	End of Week 20	End of Week 24	End of Weeks 28, 32	End of Week 36	End of Weeks 40, 44, 48	End of Week 52/EOT	28-Day Safety Follow-up	Unscheduled Visit
Study Day Window	-29 to -1	1	15 (± 3 days)	29 (± 3 days)	57 (± 3 days)	85 (± 3 days)	113 (± 3 days)	141 (± 3 days)	169 (± 3 days)	197, 225 (± 3 days)	253 (± 3 days)	281, 309, 337 (± 3 days)	365 (± 3 days)	(± 3 days)	
Informed consent A	X														
Subject demography	X														
Medical history	X														
Inclusion/exclusion criteria	X	X													
EFFICACY ASSESSMENTS															
CRISS					X		X		X		X		X	X	X
mRSS B	X	X			X		X		X		X		X	X	X
FVC B	X	X			X		X		X		X		X		X
SHAQ-DI B		X			X		X		X		X		X	X	X
Physician Global Assessment B		X			X		X		X		X		X	X	X
Patient Global Assessment B		X			X		X		X		X		X	X	X
PFTs C		X							X				X	X	X
Skin biopsies D		X							X				X		
SAFETY ASSESSMENTS															
Complete PE E	X	X							X				X	X	X
Symptom-directed PE E			X	X	X	X	X	X	X	X	X				
Vital signs F	X	X	X	X	X	X	X	X	X	X	X	X	X	X	X
Weight	X	X	X	X	X	X	X	X	X	X	X	X	X	X	X
Hematology and chemistry G	X	X	X	X	X	X	X	X	X	X	X	X	X	X	X
Urinalysis		X	X	X	X	X	X	X	X	X	X	X	X	X	X
12-lead ECG	X	X	X	X	X	X	X	X	X	X	X	X	X	X	X
Pregnancy test H	X	X	X	X	X	X	X	X	X	X	X	X	X	X	X
Study diary (dispense/collect)		X		X	X	X	X	X	X	X	X	X			X

Assessment	Screening Visit	Week 1 (Baseline)	End of Week 2	End of Week 4	End of Week 8	End of Week 12	End of Week 16	End of Week 20	End of Week 24	End of Weeks 28, 32	End of Week 36	End of Weeks 40, 44, 48	End of Week 52/EOT	28-Day Safety Follow-up	Unscheduled Visit
Study Day Window	-29 to -1	1	15 (± 3 days)	29 (± 3 days)	57 (± 3 days)	85 (± 3 days)	113 (± 3 days)	141 (± 3 days)	169 (± 3 days)	197, 225 (± 3 days)	253 (± 3 days)	281, 309, 337 (± 3 days)	365 (± 3 days)	(± 3 days)	
Study drug administration		X	X	X	X	X	X	X	X	X	X	X			X
Dispense and collect study drug		X		X	X	X	X	X	X	X	X	X			X
Collect study drug and study diary														X	
Concomitant medication															
Adverse events															

Abbreviations: CPK = creatinine phosphokinase; CRISS = Combined Response Index in Diffuse Cutaneous Systemic Sclerosis; DLCO = diffusing capacity of the lungs for carbon monoxide; ECG = electrocardiograph; EDC = electronic data capture; EOT = end of treatment; FEV1 = forced expiratory volume (in the first second); FVC = forced vital capacity; Hb = hemoglobin; ICF = informed consent form; ILD = interstitial lung disease; mRSS = modified Rodnan Skin Score; PE = physical examination; PFT = pulmonary function test; SHAQ—DI = Scleroderma Health Assessment Questionnaire—Disability Index; TLC = total lung capacity; UNS = unscheduled

- A. The ICF must be signed before any study procedure begins.
- B. mRSS, SHAQ-DI, FVC, Physician Global Assessment and Patient Global Assessment will be performed at baseline Day 1, Day 57, Day 113, and Day 169, and then after their last dose of study drug (4-Week Follow-up Visit). mRSS and FVC will also be performed at screening as one of the inclusion criteria. FVCs do not need to be repeated when done at the same time point that PFT is scheduled.
- C. PFTs, to include FEV1, FVC, DLCO (corrected for Hb), TLC, and RV, will be performed at baseline and Day 169 (± 7 days). In addition, full PFTs will be performed after their last dose of study drug (4-week Follow-up Visit). If the PFTs is performed within one month of the EOT visit, it does not need to be done again at the EOT visit.

[figure not shown]
- D. Double punch skin biopsies are mandatory for all subjects on Day 1, Day 169, and at EOT or Week 52 [REDACTED]
- E. A complete PE is to include documentation of height (screening only), weight, body temperature, and vital signs (blood pressure [sitting], pulse rate [sitting], and respiratory rate) and will be performed by a physician or staff member who is qualified to perform such examinations (e.g., physician's assistant, nurse practitioner). All PEs will include assessment of cardiac (including heart rate, vital sign), musculoskeletal (i.e., muscle aches), and neurological (i.e., gait) systems.
- F. Sitting blood pressure, heart rate to be obtained (after 5 minutes of rest)
- G. See [Section 6.2.4](#) for a complete list of laboratory safety assessments.
- H. Women of childbearing potential must have a negative urine pregnancy test. Positive results are to be confirmed with serum testing. In the event of a positive urine test at baseline, serum testing results should be acquired within 48 hours prior to study start.

Note: At Week 1 Day 1 visit, if screening was completed within 7 days of baseline, only the complete PE and vital sign measurements need to be repeated.

Note: CRISS will not be performed on site but rather will be calculated outside of EDC.

[figure not shown]

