### **1.3 BELUMOSUDIL NONCLINICAL EXPERIENCE**

In vitro, belumosudil has demonstrated an impact on the T-helper 17 (Th17) and regulatory T cells (Treg)-immune responses as well as on the actin/myosin cytoskeletal network and collagen formation. In vivo, belumosudil has demonstrated efficacy in a variety of clinically relevant animal models of disease including chronic graft versus host disease (cGVHD), scleroderma, idiopathic pulmonary fibrosis (IPF), and other autoimmune diseases.

Good Laboratory Practice (GLP) compliant rat and dog general toxicology/toxicokinetic studies of acute, subchronic (1-and 3-month), and chronic (6-month rat and 9-month dog) duration have been completed. In addition, safety pharmacology (human ether-à-go go related gene [in vitro], central nervous system [rat], respiratory [rat], and cardiovascular [dog]), embryo-fetal toxicology [rat and rabbit], male/female fertility [rat]), genotoxicity, and phototoxicity studies have also been completed. The primary nonclinical toxicology finding at/near clinically relevant exposures were limited to changes in the cardiovascular (blood pressure [BP] lowering), hepatic (transaminitis, hypertrophy/increased organ weight, and

cholestasis/inflammation), renal (increased blood urea nitrogen [BUN], tubular changes, pigmentation, intracellular protein droplets in the epithelium), gastrointestinal (decreased appetite), and hematopoietic/immunologic (anemia with regeneration and thymic/splenic lymphoid depletion) systems.

Belumosudil demonstrated embryo-fetal toxicity/teratogenicity as well as reduced male fertility (reduced fertility index/sperm concentration/motility and increased abnormal sperm percentage), and changes in the testes/epididymis (decreased organ weights and degenerative histopathology). Male fertility findings were generally at higher than clinically relevant exposures.

All pivotal non-clinical safety studies (i.e., those studies identified in International Conference on Harmonisation guidelines as needing to be conducted in accordance with GLP) were conducted in a country that is a member of the Organisation for Economic Cooperation and Development (OECD) Mutual Acceptance of Data program in accordance with the OECD Test Guidelines and Principles of GLP. Study details and potential clinically relevant findings from these studies are summarized in the belumosudil [Investigator's Brochure \(IB\)](#).

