#### 3.4 INCLUSION CRITERIA

1. Male and female subjects  $\geq$  18 years old with the diagnosis of dcSSc according to the 2013 American College of Rheumatology and European League Against Rheumatism criteria

2. Must have disease duration (defined as interval from first non-Raynaud disease manifestation) of  $\leq$  6 years
3. Must have mRSS  $\geq$  15 but  $\leq$  40
4. Must have active disease as determined by the Principal Investigator within the 6 months prior to screening
5. Adequate organ and bone marrow functions evaluated during the 28 days prior to enrollment as follows:
  - a. Absolute neutrophil count  $\geq 1.5 \times 10^9/L$
  - b. Platelet count  $\geq 100 \times 10^9/L$
  - c. Total bilirubin  $\leq 1.0 \times$  upper limit of normal (ULN)
  - d. Alanine aminotransferase (ALT), aspartate aminotransferase (AST), and serum creatinine  $\leq 1.5 \times$  ULN
6. Female subjects of childbearing potential have a negative pregnancy test at screening. Females of childbearing potential are defined as sexually mature women without prior hysterectomy or who have had any evidence of menses in the past 12 months. However, women who have been amenorrheic for 12 or more months are still considered to be of childbearing potential if the amenorrhea is possibly due to prior chemotherapy, anti-estrogens, or ovarian suppression.
  - a. Women of childbearing potential (i.e., menstruating women) must have a negative urine pregnancy test (positive urine tests are to be confirmed by serum test) documented within the 24-hour period prior to the first dose of study drug.
  - b. Sexually active women of childbearing potential enrolled in the study must agree to use two forms of accepted methods of contraception during the course of the study and for 3 months after their last dose of study drug. Effective birth control includes (i) intrauterine device plus 1 barrier method; (ii) on stable doses of hormonal contraception for at least 3 months (e.g., PO, injectable, implant, transdermal) plus 1 barrier method; or (iii) 2 barrier methods. Effective barrier methods are male or female condoms, diaphragms, and spermicides (creams or gels that contain a chemical to kill sperm), or a vasectomized partner.
7. For male patients who are sexually active and who are partners of premenopausal women: agreement to use 2 forms of contraception as in criterion number 6b above during the treatment period and for at least 3 months after the last dose of study drug.

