### 5.2.1 Week 1 Day 1 Visit (Baseline)

At the Week 1 Day 1 Visit, subjects will come to the clinic to have the following procedures:

- Confirmation of inclusion/exclusion criteria
- mRSS
- SHAQ-DI
- Physician Global Assessment
- Patient Global Assessment
- PFT\*
- Skin biopsies
- Complete PE
- Vital signs
- Weight
- Hematology and chemistry\*
- Urinalysis\*
- 12-lead ECG
- Pregnancy test
- Dispense study diary
- Study drug administration (belumosudil 200 mg): review with subject
- Dispense study drug
- Concomitant medication assessment
- AE assessment

*\*These assessments do not need to be repeated if they were conducted within 7 days of baseline.*

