3.1.5 Baseline

Baseline value is defined as the valid and last non-missing value obtained within 29 days prior to subject receiving the first study medication, unless otherwise stated under the related assessment section. Baseline can be the day before the first study medication or on the same day as the first study medication if a pre-dose assessment is available. Subjects without data on a parameter before the first study medication will have a missing baseline for this parameter.

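### The Appendix A Day 1 note lets mRSS, ECG and the pregnancy test carry over from screening, against section 5.2.1, footnote B and, for tests older than 24 hours, criterion 6a

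*Protocol*

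**What the plan says.** Four places in the protocol govern what is done on Day 1.

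- **Appendix A, note under the table:** "if screening was completed within 7 days of baseline, only the complete PE and vital sign measurements need to be repeated".
- **Section 5.2.1:** lists mRSS, 12-lead ECG and pregnancy test as Day 1 procedures without an asterisk. Only PFT, hematology/chemistry and urinalysis carry one, and the asterisk reads: "These assessments do not need to be repeated if they were conducted within 7 days of baseline".
- **Appendix A, footnote B:** the list that begins with mRSS and ends "Physician Global Assessment and Patient Global Assessment will be performed at baseline Day 1, Day 57, Day 113, and Day 169", followed by "mRSS and FVC will also be performed at screening as one of the inclusion criteria". The Day 1 score is scheduled in its own right. The screening score is additional and serves eligibility (criterion 3, mRSS 15 to 40).
- **Section 3.4, criterion 6a:** a negative urine pregnancy test "documented within the 24-hour period prior to the first dose of study drug".

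SAP 3.1.5 defines baseline as the valid and "last non-missing value obtained within 29 days prior to subject receiving the first study medication", and accepts a same-day value if it is pre-dose. SAP 3.8.1 builds CRISS from changes from baseline and sets no separate baseline rule for mRSS.

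**The concern.** Sites often work from the schedule table and its notes. A site that follows the note can skip Day 1 items that the body of the protocol and a footnote of the same appendix require. Two consequences follow.

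The first is safety. Protocol section 1.3 states: "Belumosudil demonstrated embryo-fetal toxicity/teratogenicity". Instructions on the pre-dose pregnancy test should not point in two directions. The ECG matters as well, because exclusion 1 uses QTcF and SAP 3.9.4 categorises QTcF change from baseline.

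The second is the primary endpoint. If the Day 1 mRSS is skipped, the last value before first dose is the screening score, which was selected by the entry range. Change measured from a score selected with a floor tends to show improvement even if nothing happens, and a single-arm study has no control group in which the same drift would appear. SHAQ-DI and both global assessments are not done at screening, so their baseline stays on Day 1. One subject's CRISS baseline would then mix days.

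**Working it through.** **1. Text comparison (no assumptions).** Items of interest that appear at both screening and Day 1 in the Appendix A table:

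| Item | Appendix A note | Section 5.2.1 | Other text |
|---|---|---|---|
| mRSS | need not be repeated | to be done, no waiver | footnote B: done on Day 1 |
| 12-lead ECG | need not be repeated | to be done, no waiver | none |
| Pregnancy test | need not be repeated, up to 7 days old | to be done, no waiver | criterion 6a: within 24 hours before first dose |
| Hematology/chemistry | need not be repeated | waived within 7 days | consistent |

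The first three rows conflict. The pregnancy-test conflict with 6a concerns tests between 24 hours and 7 days old; a screening test taken within 24 hours of dosing meets 6a. Weight is not a real conflict, because the complete PE, which must be repeated, includes it.

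**2. Which mRSS becomes baseline.** SAP 3.1.5 takes the last value before first dose. With a pre-dose Day 1 mRSS, that score is the baseline. Without one, the screening score is.

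**3. Size of the selection effect (assumed inputs).** The documents give no mRSS mean, SD or measurement error. Assume a true score T ~ N(μ, σb²), a screening score S = T + error with SD σe, no true change, and entry if 15 ≤ S ≤ 40. With σ = √(σb² + σe²), a = (15 − μ)/σ and b = (40 − μ)/σ:

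mean spurious change = −(σe²/σ²) × σ × [φ(a) − φ(b)] / [Φ(b) − Φ(a)]

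The grid is μ = 18, 22, 25; σb = 5, 8; σe = 2, 3, 5.

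- Smallest (μ = 25, σb = 5, σe = 2): σ = 5.385, a = −1.857, b = 2.785. Mean excess = 5.385 × (0.0711 − 0.0083)/0.9657 = 0.35; times 4/29 gives **0.05 units**.
- Largest (μ = 18, σb = 5, σe = 5): σ = 7.071, a = −0.424, b = 3.111. Mean excess = 7.071 × (0.3646 − 0.0032)/0.6634 = 3.85; times 25/50 gives **1.93 units**.

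A narrower set of assumptions (mean 18-25, SD 7-8, error SD 1-4) gives 0.02 to 1.12 units.

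**4. What a Day 1 baseline would remove.** Section 5.2.1 lists confirmation of the eligibility criteria on Day 1, but the documents do not say whether the 15-40 range is applied again to the Day 1 score.

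- Not applied again: the Day 1 error is independent of selection, the spurious change is about 0, and the whole effect is removed.
- Applied again: by simulation on the same grid, 0.03 to about 1.5 units remain. The reduction runs from 0.05 − 0.03 = 0.02 units (μ = 25, σb = 5, σe = 2) to 1.52 − 1.01 = 0.51 units (μ = 18, σb = 8, σe = 5).

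**5. Weight of one mRSS unit in CRISS.** The SAP 3.8.1 coefficient is −0.81, so a one-unit fall multiplies the odds by exp(0.81) = 2.25. A score of 0.20 becomes 0.36, and 0.41 becomes 0.61. With 12 to 15 subjects, one subject is 1/15 = 6.7 to 1/12 = 8.3 percentage points of a response rate.

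**The case against.** The strongest reply is that the note is permissive, applies only when screening falls within 7 days of Day 1 (the window runs from Day −29 to −1), and is outweighed on mRSS by section 5.2.1, the Day 1 mark in the table and footnote B. A reader might infer that the qualifying score is the CRISS baseline for the trial as a whole. The documents do not support that: it can be so only for subjects screened within 7 days whose site relies on the note, and nothing says how many there would be.

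A reader might also infer a fault in the SAP. There is none on this point. SAP 3.1.5 already uses a pre-dose Day 1 value when one exists, so the fault lies in the protocol note. Nor can a material inflation of the week-24 CRISS60 rate be inferred. That would need the spread of all five CRISS components and the fraction of subjects affected, neither of which is given. The upper end of the mRSS range needs half the variance in scores to be measurement error.

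On pregnancy testing, the note waives procedures, not eligibility. Criterion 6a remains mandatory, section 3.6 requires all criteria to be met, and eligibility is confirmed on Day 1. It would go too far to say that the protocol permits dosing without a valid test.

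All of this stands and limits the consequences. It does not remove the contradiction, which lies in the text and includes one within Appendix A itself.

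**Conclusion.** The note is wrong as written. It conflicts with section 5.2.1 on mRSS, ECG and pregnancy test, with footnote B on mRSS, and with criterion 6a for pregnancy tests older than 24 hours. That conclusion needs no assumptions, and it is the reason to act.

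The effect on the primary endpoint is conditional and secondary. In affected subjects only, a screening baseline would add about 0.05 to 1.9 mRSS units of apparent improvement. This rests on an assumed mean of 18-25, between-subject SD of 5-8, error SD of 2-5, normal errors and no true change. A Day 1 baseline removes all of it, or only about 0.02 to 0.5 units if the Day 1 score must also lie within 15-40. The effect may be small, and the study is descriptive and exploratory, so no figure for the CRISS60 rate is offered.

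**What to change.** 1. **Protocol:** reconcile the Appendix A note with section 5.2.1, footnote B and criterion 6a, so that sites have one consistent Day 1 instruction. Which pregnancy-test and ECG timing applies is for the sponsor to settle.
2. **Protocol, for the analysis:** take mRSS out of the note's carry-over, so that the Day 1 score already scheduled in 5.2.1 and footnote B is obtained before dosing. SAP 3.1.5 then uses it as baseline without a change to the definition.
3. **SAP or dataset specification:** flag any subject whose mRSS baseline is the screening value, so that the reader of the CRISS results can see how many there are.

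The cost is one protocol clarification and one flag. No new visit, procedure or data item is needed.
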